9.2.1 Materials for Swab Collection for Resistance Testing

Swabs

NP specimens will be collected using sterile, individually-wrapped pediatric flocked swabs with a plastic swab shaft (manufactured by Copan). Nasal sites will be swabbed with a sterile, Dacron polyester-tipped swab with a plastic shaft (manufactured by Fisherbrand).

Sample Tubes

All field samples for DNA testing will be collected into sterile 2.0ml microcentrifuge tubes, manufactured by Sarstedt®. (DNA-free tubes will be used for collection in DNA/RNA shield.)

Cooler Bags with Frozen Ice Packs

Insulated cooler bags will be used to carry samples to and from the field. In addition, frozen gel ice packs designed to thaw slowly will be used to maintain the temperature in the cooler bags during transport.

-20°C Freezer

A standard -20°C freezer located at the local health center will be used strictly for the storage and freezing of ice packs and samples. This freezer is kept in a locked room on the grounds of the Health Center, which is under 24-hour security guard supervision.

9.2.2 Protocol for Tubing and Handling of Samples

The tubing and handling protocol must be carefully followed in order to prevent contamination and ensure the safe transport of the samples back to the local microbiology laboratory and/or to the US for processing. The person in charge of labeling, tubing, arranging, and handling the samples needs to perform this task in the most orderly and attentive manner.

- Both hands of the tuber should be gloved at all times. The tuber's gloves only need to be changed when any potential contamination of the gloves occurs. The tuber opens the capped, hinged lid of a microcentrifuge tube, which has been labeled with the participant's random identification number.
- 2. The swab is inserted by the examiner into the microcentrifuge tube held by the tuber. The swab shaft should only be inserted until the swab head is fully in the tube. The tuber will cut the swab shaft with sterile scissors.
- 3. The tuber should screw the cap of the microcentrifuge tube tightly, flick the tube to mix the sample with the media (for tubes with DNA/RNA shield media), and place it in the sample collection box, located in the cooler bag filled with frozen ice packs. The flap of the cooler bag should be closed between each patient. The cooler bag should be in as cool a place as possible in the field, in a shaded area out of the sun.

Upon returning from the field each day, the samples in STGG will be immediately taken to a local health center and stored in a commercial -20°C freezer, reserved solely for storage of specimens and ice packs. All samples will be in sample boxes, labeled with the village name for easy future identification.

9.3 Stool Samples

All study sites will collect either stool samples or rectal swabs for resistance testing, but methodology will depend upon the type of samples collected and consist of either culturing/microbiological testing or nucleic acid based testing.

Rectal Swabs for Culturing/Microbiological Testing

Rectal swabs will be collected and placed into Amies transport media or Norgen Stool Preservative. We will use standard microbiologic techniques to isolate *Escherichia coli*. Resistance to azithromycin, ampicillin, and co-trimoxazole will be determined. Isolates can be further classified into commensal and diarrheagenic subtypes using a multiplex PCR assay.⁴³

Stool Samples for Nucleic Acid Based Testing

Stool specimens will be used to look for the presence of E. coli and macrolide resistant determinants typically associated with resistant strains of E. coli, using a resistome approach. This will be carried out by isolating DNA from stool specimens and detecting the presence of E. coli as well as genes associated with antibiotic resistance (i.e. *erm*, *mef*, *and mph* genes) via PCR assays.⁴⁵ Other possible experiments may eventually include using PCR to detect the presence of toxins or virulence factors (i.e. *eae*, *stx*, *bfp-A*, *VT-1*, *VT-2*), which are linked to diarrheagenic E. coli strains, ⁴⁶⁻⁴⁷ or exploring the complete microbiome of the stool specimens.

9.3.1 Stool Specimen Collection

Rectal Swab Collection for Culturing/Microbiological Testing

The test will require that the child's parent and examiners work together to obtain a good sample. Is it important to describe the test to the parent so that they can best assist with keeping the child still during the procedure, if necessary.

In place of stool specimens, rectal swabs can be collected in the following way:

- 1. Put on a clean pair of gloves.
- 2. Partially open the fecal swab package and remove the top section of the collection vial (this can be discarded).
- 3. Position the child:
 - Lie the child on his/her back, hold legs in the air (it is useful to have assistance).
 - Or have the child lay on his/her stomach across the mother/guardian's lap
- 4. Remove the swab from the package. Take care that the cotton tip is not touched. If it is touched, throw the swab away and begin with a new one.

- 5. Insert the tip of the swab into the child's anus only as far as needed to contact fecal material (1-3cm) and rotate 180 degrees. The tip should be a brownish color when removed.
- 6. Place swab into the preservative in the collection tube. Make sure the swab is fully submerged in the liquid preservative and then break the swab off using the pre-scored breaking point.
- 7. Screw the cap back on the tube and make sure that it's tightened. Wrap the area where the cap meets the tube with Parafilm to ensure that the sample will not leak, and then place the tube into the appropriate sample box.
 - If the swab cannot be broken off while the tip is fully submerged in the liquid, try twirling the swab in the liquid first (to release the contents of the sample into the preservative) before breaking it off. Avoid rubbing the sample on the tip of the swab off on the side of the tube where there is no liquid.
- 8. Place a random number label on the collection tube.
- 9. Place the tube the rectal swab container.
- 10. **Swab storage for Genetic analysis:** Store samples at room temperature. According to the manufacturer, the preservative in the tube will preserve DNA for 5 months at room temperature (7 days for RNA), and thereafter can be frozen (-20°C or -80°C) for long-term storage.

Stool Specimen Collection for Nucleic Acid Based Testing

For the study participant/parent of the child:

- 1. Collect the initial stool specimen on a piece of plastic.
- 2. Transfer a few heaping spoonfuls of the fresh stool into the smaller, 4 oz disposable plastic container that has a locking lid, using the spoon provided. Return this to the trained field worker.

For the trained field worker:

- 1. Wearing fresh gloves, carefully place a portion of the stool sample from the disposable 4 oz plastic container into a labeled Norgen Stool Nucleic Acid Collection and Transport Tube (15 ml collection tube that contains preservative), using the small spatula that is attached to the tube's cap. Fill up to the line as indicated by the tube.⁴⁴ Make sure to spoon the stool into the tube without touching the rim or outside of the tube to avoid any contamination.
- 2. Once the stool sample has been added, place the cap tightly back onto the tube
- 3. Mix gently until the stool is well submerged under the preservative. Do not shake the tube up and down, just gently swirl.
- 4. Wrap the lid of the tube with a piece of Parafilm to seal it.

- 5. Place the tube into the storage box and store at room temperature.
- 6. Once the final stool sample has been collected in the Norgen Stool Nucleic Acid Collection and Transport Tube, wrap up the initial stool sample in the large receptacle container using the plastic lining and properly dispose of it. Also, dispose of the stool sample in the 4 oz plastic container and the spoon that was used.

9.3.2 Materials for Stool Specimen Collection

Rectal Swab Collection for Culturing/Microbiological Testing Swab

An individually-wrapped Copan flocked swab with a plastic shaft will be used to collect the rectal swab and then placed into a Stool Nucleic Acid Collection and Transport Tube containing Norgen Stool Preservative or Amies Transport Medium.

Sample Tube with Media

The specimen will be in a sterile Stool Nucleic Acid Collection and Transport Tube containing Norgen Stool Preservative or Amies Transport Medium with a cap that will be tightened firmly.

Stool Specimen Collection for Nucleic Acid Based Testing Plastic Lining

Each participant will be given a piece of plastic that will be placed on the ground to collect the initial stool sample.

Spoon

Wooden medical spoon used to transfer a portion of the initial stool specimen to the small plastic container, which will be brought to the trained field worker by the parent.

Small Plastic Container

4 oz disposable plastic container with locking lid used to transport a portion of the initial stool specimen to the trained field worker.

9.4 Quality Control Measures for Specimen Collection

Negative Field Controls

Negative field control swabs for NP and stool will be taken in each community to assess for contamination: one control swab each (NP and stool/rectal) are taken

before specimen collection begins in a community; and another (NP and stool/rectal) upon completion of specimen collection.

- 1. For each negative field control, the examiner will open a new swab as described above.
- 2. Wave the swab in the air, without making contact with anyone/anything.
- 3. Tube the swab in media, as described above.

Duplicate swabs

Duplicate NP swabs and rectal swabs/stool specimen will be collected from two children per community.

Chapter 10: Cost-Effectiveness

10.1. Costs

We will record the costs of distributions in a random subset of 12 villages at MORDOR 6 or 12 and MORDOR 24. We will assume a societal perspective. Programmatic costs will be included, such as: azithromycin, antibiotic distributors, supervisors, drivers, fuel, and the time of community volunteers, and the costs of azithromycin will be estimated using the market price for generic formulations. See appendix for the study forms to be used. Collection of certain costs will be incorporated into the electronic data capture system, including the duration of time that the antibiotic distributors worked, the number of antibiotic distributors per team, the number of doses of azithromycin/placebo given, and the number of doses of azithromycin/placebo wasted. Other costs will be collected on paper forms from the appropriate parties: the drivers will complete paper forms describing costs of fuel and automobile maintenance, and the study coordinator will complete paper forms describing the costs of consumables purchased for the study, as well as the overhead costs of maintaining the mass drug administration office.

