MORDOR 6 Aug-15 to Jan-16	Census Verbal Autopsy Azithro	Census Verbal Autopsy Placebo	Census Azithro NP Swabs, Blood, Stool ^a Malaria Collection ^b	Census Placebo NP Swabs, Blood, Stool ^a Malaria Collection ^b
MORDOR 12 Feb-16 to Jul- 16	Census Verbal Autopsy Azithro	Census Verbal Autopsy Placebo	Census Swabs Blood Stool Anthropometry Azithro	Census Swabs Blood Stool Anthropometry Placebo
MORDOR 18 Aug-16 to Jan-17	Census Verbal Autopsy Azithro	Census Verbal Autopsy Placebo	Census Azithro NP Swabs, Blood, Stool ^a	Census Placebo NP Swabs, Blood, Stool ^a
MORDOR 24 Feb-17 to Jul- 17	Census Verbal Autopsy Azithro^C	Census Verbal Autopsy Azithro^C	Census Swabs Blood Stool Anthropometry Azithro ^C	Census Swabs Blood Stool Anthropometry Azithro ^C

Only children aged 1 month to 60 months per community will be treated

Arms Azithro+ & Control+: swabs, blood testing, and stool samples or rectal swabs from 40 randomly selected children aged 60 months per community; anthropometry from a cohort of children aged 1 to 60 months per community; NP swabs from 40 individuals aged 7 - 12 years (Niger only)

a: Tanzania only

b: Niger only

c: Decision to treat ALL communities with azithromycin at 24-months if there is a significant mortality difference (in preparation for possible contingent study, Niger only)
*: +/- 1 month

Chapter 5: Core and Non-Core Study Elements

An overview of core and non-core elements for the mortality and morbidity study is provided here, but will be described in more detail in the following chapters.

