5.1. Mortality Study

5.1.1. Core Elements (Malawi, Niger, and Tanzania)

In all three study sites, we will conduct the following study activities for the mortality study:

Training

Before the baseline visit, the University of California San Francisco (UCSF) team will certify local team members at all three study sites. Standardization activities before each biannual census will consist of didactic classroom instruction and mock census activities, followed by in-field training to harmonize protocols.

Census

An enumerated population census for 0 – 60 month olds (focusing on this age group) will be conducted every 6 months by trained field workers masked to study arm, recording births, deaths, and migration of children eligible for treatment. Pregnant women will be noted at each census, to maximize inclusion of newborns on the subsequent census.

Random Census Verification

A repeat census will be conducted in a random selection of households at each study visit. Personnel will be different from the original census. This will allow us to assess whether the census team identified all births, deaths, and migratory episodes relative to the previous census.

Verbal Autopsy

Each of the study sites will perform a verbal autopsy for all children (aged 1-60 months) identified as having died during the study.³⁹

Treatment

Children aged 1-60 months on the current census will be offered weight- or height-based (<1 year weight and children who cannot stand; ≥1 year height), directly observed, oral azithromycin suspension (or oral placebo) every 6 months for 2 years as performed in trachoma programs in each of the 3 countries. Specifically, individuals are eligible on or after their one month birthday, and prior to the day of their fifth birthday.

Antibiotic Coverage Surveillance

We will estimate antibiotic coverage from the most recent biannual census records. At the end of each treatment round at months 6, 12, and 18, we will identify any children who have missed 2 or more consecutive treatments, and forward this information to the census team.

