5.2. Morbidity/Resistance Study

5.2.1. Core Elements (Malawi, Niger, and Tanzania)

All core elements described in 5.1.1 will also be conducted in the morbidity / resistance study. The enumerated population census for the morbidity / resistance communities will include 0-12 year olds.

The designation "core elements" means that all study sites will be performing the study activity.

In all study sites, we will perform the following tests on a random sample of 40 children aged 1-60 months from each Azithro-Plus and Control-Plus community at baseline, 12, and 24 months:

- Blood samples (dried blood spots optional) for malaria and anemia
- Nasopharyngeal swabs for pneumococcal macrolide resistance
- Stool samples or rectal swabs to assess for macrolide resistance
- Assessment of costs of a census and mass drug administration (at 6 or 12 and 24 month visits only)

Samples will be processed in-country when possible; otherwise they will be shipped to UCSF.

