5.2.2. Non-core Elements

The designation "non-core" element means that study sites may choose if they wish to perform the study activity. If the study sites perform the study activity, the methodology will be performed according to this protocol so that the 3 sites may be more easily compared. Sites may choose to perform several non-core morbidity assessments at the 0, 12, and 24 month visits:

- Nasal swabs for macrolide resistance in *Staphylococcus aureus*
- Conjunctival swabs for Chlamydia trachomatis
- Conjunctival examination and photography to assess for trachoma
- Anthropometric assessments
- Nasopharyngeal swab collection at local health posts to compare macrolide resistance in the community with that in the health post

In addition, there are several non-core activities that occur outside the annual morbidity/resistance assessment:

- Additional study visit during the first malaria season to collect blood samples for malaria and anemia testing
- Clinic-based case finding for childhood illnesses at all health clinics in the study area

Costs

We anticipate recording the cost of distributions in a random subset of 12 villages at the 6 or 12 and 24 month visits.

Details of the non-core elements for each study site can be found in the Appendices.

Chapter 6: Census

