- 12. Subgroup analysis of children eligible for 4 treatments, but receiving only 1, 2, 3, or 4 treatments by arm (1 vs. 1, 2 vs. 2, 3 vs. 3, and 4 vs. 4 treatments).
- 13. A secondary analysis will be conducted on every child who died and had a treatement (antibiotics or placebo) assessing if:
 - a. The time of death differs between arms (within a year), using a test of equality of circular distributions (using the phase angle as the outcome variable), with a supplementary comparison conducted by fitting negative binomial regression based on linear predictor $A_i \sin (\theta t + \phi)$, where the null hypothesis is that the phase offset ϕ is independent of treatment (similarly, we may compare equality of circular means using a two-sample Edwards test). Note that in this analysis, a test of the equality of the amplitude A_i will also be reported. We will conduct goodness of fit tests using higher order trigonometric terms.
 - b. The time between treatment and death differs between treatment arms will be compared by performing a survival analysis that accounts for country. Note that in order to do a survival analysis, we will include children that survived in the analysis.

- c. The times of treatment (in children that died) between the two arms a Wilcoxon rank sum test comparing the time of treatment in the deceased between the two groups using the Wilcoxon rank sum test.
- 14. Spatial analysis. Secondary analysis will include geographic region as follows. First, we will present a plot of the reduction in mortality by region within country (e.g. zone in Malawi) versus the mortality rate in the placebo communities in that region. This will be done across all countries. Additional data (poverty indices) may be included in such analyses. Such analyses, exploratory in nature, will be sharply distinguished from prespecified outcomes.
- 15. Analyses will be reported using dose (or recorded height/weight as applicable). We will also conduct models in which the number of received treatments is used as a predictor. This is a secondary analysis.

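### The second distribution-costing round is set at month 24, when Malawi and Tanzania have no scheduled distribution and Niger has only a conditional one

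*Protocol*

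**What the plan says.** Three places in the Protocol fix the costing visits.

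- 10.1 Costs: "We will record the costs of distributions in a random subset of 12 villages at MORDOR 6 or 12 and MORDOR 24". The items it names include distributors' working time, team size, doses given, doses wasted, fuel and vehicle upkeep.
- 5.2.2 anticipates "recording the cost of distributions in a random subset of 12 villages at the 6 or 12 and 24 month visits".
- 5.2.1 lists, among the core elements, "Assessment of costs of a census and mass drug administration (at 6 or 12 and 24 month visits only". Its last word rules out other visits, and its scope covers the census as well as the distribution.

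The treatment schedule is given elsewhere.

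- Protocol 4.2 divides the study into four six-month segments, each opened by one census and closed by the next. Month 24 closes the fourth.
- Protocol 5.1.1 places the coverage checks "At the end of each treatment round at months 6, 12, and 18".
- SAP 2.1.1, secondary analysis 12, takes full exposure to be children "eligible for 4 treatments".
- In Protocol 4.3, Table 1 shows treatment without condition at months 0, 6, 12 and 18. The mortality columns at month 24 read "Census Verbal Autopsy Azithro^C". Note c explains the mark: "Decision to treat ALL communities with azithromycin at 24-months if there is a significant mortality difference", with the addition "in preparation for possible contingent study, Niger only".

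**The concern.** A visit without a distribution has no distribution cost to record. Read against Table 1, the second costing round in Malawi and Tanzania has only a census to measure. In Niger, whether there is a distribution to cost depends on the mortality result.

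Objective 2 is the cost-effectiveness of mass azithromycin. The plan provides for a repeat measurement of distribution cost, but two of the three countries would have one measurement only. In Niger, the amount of cost information would depend on the same effect with which it is to be combined. The documents do not say what to do with month 24 costing data when nothing was distributed.

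**Working it through.** The plan gives no figure to reproduce here. The check compares two schedules and then counts village-rounds.

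**Step 1: costing visits against distributions.**

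| Visit | Distribution (Table 1) | Distribution costing (5.2.1, 5.2.2, 10.1) |
|---|---|---|
| Month 0 | all arms | no |
| Month 6 | all arms | first round, here or at month 12 |
| Month 12 | all arms | first round, here or at month 6 |
| Month 18 | all arms | no |
| Month 24 | conditional (note c) | second round |

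The unconditional rounds number four. This agrees with the four segments in 4.2, the coverage checks in 5.1.1 and the four treatments in the SAP.

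**Step 2: which countries could distribute at month 24.** Note c carries a condition and a country limit. In the SAP for the Contingency Study, sections 1 and 2 agree with both: further treatment follows only if the primary analysis shows benefit, and the communities then treated at the 24 month visit are those in Niger. On this reading Malawi and Tanzania have no distribution at month 24, and Niger has one only if the result is positive.

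**Step 3: village-rounds lost.** The formula is villages per country × rounds × countries. The documents do not say whether the 12 villages are per country or in total, so both cases are shown as assumptions.

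| | 12 per country | 12 in total, 4 per country |
|---|---|---|
| Planned | 12 × 2 × 3 = 72 | 4 × 2 × 3 = 24 |
| Of these, at month 24 | 12 × 1 × 3 = 36 | 4 × 1 × 3 = 12 |
| Lost if Niger distributes | 12 × 2 = 24; 24/72 = 33% | 4 × 2 = 8; 8/24 = 33% |
| Lost if Niger does not | 36/72 = 50% | 12/24 = 50% |

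By country, the loss is 1 round of 2 (50%) in Malawi and in Tanzania, and 0 of 2 or 1 of 2 in Niger. These country figures depend neither on the number of villages nor on how many sites carry out costing.

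**Step 4: the other reading of note c.** Table 1 prints the month 24 entry with no country split, and the words limiting it to Niger could belong to the contingent study alone. Month 24 treatment would then be conditional in all three countries, and the loss would be 0/72 = 0% or 36/72 = 50%. On neither reading is a month 24 distribution assured.

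**Step 5: which items are affected.** Protocol 14.4 has the treatment status and dose of each child recorded during every mass distribution, so doses given do not depend on a costing visit. Under 10.1 the drug is priced at the generic market price, which does not depend on the visit either. The items tied to a costed round are mainly distributor hours, team size, wastage and transport. Census costs, which 5.2.1 also covers, can be collected at month 24 in every site.

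**The case against.** The strongest reply is that this is a small scheduling slip in a secondary objective. Month 24 is a real costing visit, because a census takes place then in every site and arm. The first costing round is unaffected, and the doses are known for all rounds. Costing also appears in 5.2.2 under the non-core heading, where sites may choose, as well as among the core elements in 5.2.1. The costing forms and site appendices could settle the matter, and they are not in the documents at hand. All of this stands, and it limits how far the point reaches. It does not supply a distribution to cost at month 24 in Malawi or Tanzania.

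A reader might infer more than the documents support:

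- **That half of the distribution-cost data is certainly lost.** Half is the trial-wide upper bound. It becomes 33% if Niger distributes at month 24.
- **That only an early round would ever be costed.** The first costing may be at month 12, which is the third of four distributions.
- **That cost per distribution would be understated by averaging in census-only visits.** Nothing in the plan proposes such averaging.
- **That a costed month 24 round in Niger would be entirely azithromycin.** Table 1 suggests this, but the Contingency Study SAP, under Morbidity Study, keeps the morbidity communities on placebo. Those passages need reconciling. For costing, a distribution takes place either way.
- **That twice-yearly treatment over two years implies a fifth round at month 24.** Table 1, 4.2, 5.1.1 and the SAP all point to four.

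**Conclusion.** The point holds as a conflict between the costing schedule and the treatment schedule. As written, one of the two planned distribution-cost rounds cannot be collected in Malawi or Tanzania, and in Niger it depends on the trial result. Trial-wide, 33% to 50% of planned village-rounds are lost.

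That range assumes an equal number of costed villages in each country, costing at all three sites, and the reading of note c that the SAP supports. On the other reading it is 0% to 50%. The plan loses its repeat measure of labour, wastage and transport. It keeps a first measure of these, the dose counts and the census costs. Objective 2 is affected and the primary mortality analysis is not. The plan should be corrected, but the correction is not critical.

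**What to change.** In Protocol 5.2.1, 5.2.2 and 10.1, move the second distribution-costing round from MORDOR 24 to MORDOR 18, the last round scheduled without condition in all arms. Keep MORDOR 24 for census costs only, and state that these do not enter the cost-per-distribution estimate. In the same edit, say whether the 12 villages are per country or in total.

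The cost is wording in three places. Villages, forms and the number of distribution-costing rounds stay the same, and no treatment schedule changes. The downside is that the second round comes six months earlier. The gap between the two rounds falls from 18 to 12 months if the first is at month 6 (24 − 6 against 18 − 6), and from 12 to 6 months if it is at month 12 (24 − 12 against 18 − 12).
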